8.2. Exclusion Criteria

Subjects meeting any of the following criteria must not be included in the study:

1. Has a history of a psychiatric disorder such as schizophrenia, bipolar disorder or major depression according to the criteria of the most current version of the Diagnostic and Statistical Manual of Mental Disorders (DSM). Mild depression or history of depression that is stable on treatment with a SSRI or SNRI medication at a stable dose is acceptable.

2. History of a seizure disorder, if stable on medication is acceptable.
3. Has a history or current evidence of long QT syndrome, Fridericia's formula corrected QT (QTcF) interval \geq 450 ms for men and 460ms for women, or torsades de pointes.
4. Has bradycardia (<50 bpm) or tachycardia (>100 bpm) on the ECG at screening.
5. Has uncontrolled Type-1 or Type-2 diabetes. A subject with HbA1c levels up to 7.5% can be enrolled if the investigator believes the subject's diabetes is under control.
6. Has clinically significant renal (CKD-EPI <60 mL/min/BSA (body surface area)) or hepatic impairment (ALP > 2.0 ULN and/or total bilirubin > 2.0 ULN).
7. Has any clinically significant abnormal laboratory values. Subjects with liver function tests (aspartate aminotransferase [AST] or alanine aminotransferase [ALT]) greater than twice the upper limit of normal will be excluded.
8. Is at imminent risk of self-harm, based on clinical interview and responses on the C SSRS, or of harm to others in the opinion of the Investigators. Subjects must be excluded if they report suicidal ideation with intent, with or without a plan or method (e. g. positive response to Items 4 or 5 in assessment of suicidal ideation on the C SSRS) in the past 2 months, or suicidal behavior in the past 6 months.
9. Has cancer or has had a malignant tumor within the past year, except subjects who underwent potentially curative therapy with no evidence of recurrence. (Subjects with stable untreated prostate cancer or skin cancers are not excluded).
10. Alcohol / Substance use disorder, moderate to severe, in the last 5 years according to the most current version DSM.
11. Participation in another clinical trial with an investigational agent and have taken at least one dose of study medication, unless unblinded on placebo, within 60 days prior to the start of screening. The end of a previous investigational trial is the date the last dose of an investigational agent was taken, or five half-lives of the investigational drug, whichever is greater.
12. Subjects with learning disability or developmental delay.
13. Subjects whom the site PI deems to be otherwise ineligible.
14. Subjects with a known allergy to the investigational drug or any of its components. Here are all the inactive ingredients of the IMP:

Silicified Microcrystalline Cellulose
Dibasic Calcium Phosphate Dihydrate
Mannitol
Magnesium Stearate
Hypromellose (capsule shells structure)
Titanium Dioxide (opacifier of the capsule shells)

15. Subject is currently pregnant, breast-feeding and/or lactating.

16. Subject is currently taking strong or moderate CYP3A4 inhibitors and/or inducers. See examples below:

CYP3A4 inhibitors	Itraconazole, Ketoconazole, Azamulin, Troleandomycin, Verapamil
CYP3A4 inducers	Rifampicin

17. Subject is currently receiving deep brain stimulation treatment.

9.0 DESCRIPTION OF STUDY VISITS

Each subject will have a 42-day screening period followed by 6 months of treatment at home. The study visits are described below and outlined in the Schedule of Events in [Appendix 1](#).

9.1. Screening Visit

The screening visit should occur up to 42 days before the baseline visit. The screening visit procedures may be completed over multiple days. Participants do not need to stop their Parkinson's disease SOC medications for screening visit.

Potential participants must sign an informed consent form prior to administration of any study-related procedures. Information regarding the subject's demographics, concurrent medications, and medical history will be collected along with cognitive assessments, physical examination, and neurological examination. With investigator's permission, lab re-testing is allowed within a month. If investigator deems re-screening is justified, they must contact Medical Monitor and sponsor for discussion at case-by-case basis.

Safety assessments will include an ECG that will need to be read locally and reviewed by the site investigator to confirm eligibility. The clinical safety laboratory blood and urine tests will be sent to a central lab for analysis. The screening safety laboratory tests will be comprised of a metabolic panel, complete blood count, and urinalysis as listed in Section 12.1.3. Urine dipstick

pregnancy test will be completed for female subjects. Fasting is required for safety laboratory tests.

Cognitive and functional assessments should not be administered when the subject is in a fasted state. Once all screening visit procedures are completed, all information related to eligibility, including screening lab results, must be reviewed by the site investigator to assess the subject's eligibility before proceeding to Baseline.

9.2. Baseline Visit

Baseline procedures include functional, cognitive, and behavioral assessments, safety assessments, and review of concurrent medications and potential adverse events that might occur. Fasting is required for safety laboratory tests. Participants should stop all Parkinson's disease SOC 12 hours prior to the visit to ensure a clinical OFF-state. For patients who are not on any Parkinson's disease SOC, their natural state will be considered OFF-state and since they won't have ON-state, it should be documented accordingly in the source documents.

Baseline visit should be completed in one day except for the intense PK sub-group.

Day 1:

Subjects should arrive fasted in the morning after an overnight fast. Clinical safety labs will be drawn and sent to the central lab for analysis.

After safety lab, patients will be provided low-fat light meal before completing functional and cognitive evaluations (completed in an OFF state after holding PD meds for 12 hours prior to arrival at site), a physical and neurological exam, collecting vital signs, ECG, and reviewing and recording adverse events and concurrent medications. Sites should take detailed notes of contents of all meals provided to the patients. Following completion of all these procedures, subjects who continue to meet all protocol inclusion criteria and no exclusion criteria should be randomized. Patients can take their SOC medication at this point if needed.

For sparse PK group (i.e. any subject that is not participating in the intense PK sub-study), if no medical or compliance concerns are identified, the subject will move on to the PK sampling phase, which will entail the following procedures:

- 1) Collect initial samples of blood (hour 0) with venipuncture unless PI deems inappropriate.
- 2) Administer first dose of assigned study drug after the hour 0 sampling.
- 3) Collect blood (10mL) at the 1.5hr timepoint. Blood should be taken within \pm 10 mins of times.
- 4) Perform the final safety monitoring.

For sparse PK group, prior to discharge from the clinic, vital signs should be recorded, and a review of AE(s) and concomitant medications should be conducted as the final safety monitoring. Patients will be educated of the study drug compliance and study drug return. Upon determination by the Investigator (or qualified designee) that the subject is stable, the participant will be discharged. If a participant experiences an unstable AE, the PI shall manage the event without prior consulting with the Medical Monitor. The MM shall be informed as soon as possible, and the management of the AE shall be reported in the Study documents.

For intense PK group, if no medical or compliance concerns are identified following the Day 1 procedures, subjects will be scheduled for the next day PK sampling, unless patients prefer to finish PK in one day.

Day 2 (Intense PK group only)

Patient should arrive in clinic fasted in the morning after an overnight fast but does not need to be in OFF state. The subject will start PK sampling phase, which entails the following procedures.

1. Place an intravenous line for blood sampling.
2. Collect initial sample of blood (hour 0).
3. Administer first dose of assigned study drug after the hour 0 sampling.
 - a. For 16 subjects per group, blood samples (10mL) will be collected at 1hr, 1.5hr, 2hr, 3hr, 4hr, 5hr, 6hr, 7hr, 8hr, 9hr, and 10hr timepoints. Blood should be collected within \pm 10 mins of scheduled times.
 - b. Perform periodic safety monitoring during the collection period. Participants should be asked about pain, redness or swelling at the blood collection site.
 - c. Patients will be provided low-fat light meals after 2hr, 6hr and 10hr PK sampling. Sites should take detailed notes of contents of all meals provided to the patients.
4. Perform the final safety monitoring.

Prior to discharge from the clinic, vital signs should be recorded, and a review of AE(s) and concomitant medications should be conducted as the final safety monitoring. Patients will be educated of the study drug compliance and study drug return. Upon determination by the Investigator (or qualified designee) that the subject is stable, the participant will be discharged. If a participant experiences an unstable AE, the PI shall manage the event without prior consulting with the Medical Monitor. The MM shall be informed as soon as possible, and the management of the AE shall be reported in the Study documents.

9.3. ONSITE VISIT AT 1 MONTH, 2 MONTH AND 3 MONTHS

At 1 month, 2 months and 3 months (+/- 7 days) from the baseline visit, a clinic visit should occur. Participants should stop all Parkinson's disease SOC 12 hours prior to the visit to ensure a clinical OFF-state. Clinic visit procedures include functional, and behavioral assessments, safety assessments, and review of concurrent medications and adverse events that occur in clinic and during blood collection. Fasting is required for safety laboratory tests. After safety lab, patients will be provided low-fat light meal before completing functional and cognitive evaluations (completed in an OFF state after withholding PD meds for 12 hours prior to arrival at site), a physical and neurological exam, collecting vital signs, ECG, and reviewing and recording adverse events and concurrent medications. Sites should take detailed notes of contents of all meals provided to the patients.

Study medication compliance will be reviewed and discussed, and reminders given about the upcoming end of trial visit.

A post-visit safety phone follow up will be conducted approximately 24 hours following each clinic visit.

9.4. 4.5 months Telephone Contact

A telephone call will be conducted at 4.5 months +/- 7 days from the baseline visit to assess for any changes in status, adverse events, or concomitant medications. Study medication compliance will be discussed, and reminders given about the upcoming end of trial visit.

9.5. End of Trial Visit

End of trial is when the last subject of the study finishes last clinical visit. End of trial visit is each subject's last clinical visit during the study. The end of trial visit should occur 6 months +/- 7 days following the first dose of study medication. A pre-visit phone call will be conducted 1-3 days prior to admission and a post-visit phone follow-up will be conducted approximately 24 hours following discharge. End of trial visit procedures include functional, and behavioral assessments, safety assessments, and review of concurrent medications and adverse events that occur in clinic and blood collection. Participants should stop all Parkinson's disease SOC 12 hours prior to the visit to ensure a clinical OFF-state.

9.5.1. Pre-visit Telephone Contact

A telephone call will be conducted at 1-3 days prior to end of trial to assess for any changes in status, adverse events, or concomitant medications. Study medication compliance will be discussed, and reminders given about the upcoming end of trial visit.

9.5.2. End of Trial Visit

This constitutes the subjects' last clinical visit during the study for all patients who have participated over 5 months. Early drop-out patients will be invited to participate early discontinuation visit. The end of trial visit will consist of the following: admission procedures, Time 0 blood

sampling, administration of last dose of study drug, 1.5hr after-dose blood sampling except for the subgroup of subjects participating in the intense PK sub-study, who will have PK samples for 10 hours, all psychometric and safety tests, and discharge procedures. Fasting is required for safety laboratory tests. End of trial visit should be done in one day except for the intense PK subgroup.

For the subgroup of subjects who will have intense PK samples, blood samples will be drawn at 0hr, 1hr, 1.5hr, 2hr, 3hr, 4hr, 5hr, 6hr, 7hr, 8hr, 9hr, and 10hr timepoints.

Day 1:

Subjects should arrive fasted in the morning after an overnight fast. Clinical safety labs will be drawn and sent to the central lab for analysis.

After safety lab, patients will be provided low-fat light meal before completing functional and cognitive evaluations (completed in an OFF state after holding PD meds for 12 hours prior to arrival at site), a physical and neurological exam, collecting vital signs, ECG, and reviewing and recording adverse events and concurrent medications. Sites should take detailed notes of contents of all meals provided to the patients. Patients can take their SOC medication at this point if needed.

For sparse PK group, if no medical or compliance concerns are identified, the subject will move on to the PK sampling phase, which will entail the following procedures:

- 1) Collect initial samples of blood (hour 0) by venipuncture unless PI deems inappropriate.
- 2) Administer last dose of assigned study drug after the hour 0 sampling.
- 3) Collect blood (10mL) at the 1.5hr timepoint. Blood should be taken within \pm 10 mins of times.
- 4) Perform the final safety monitoring.

For sparse PK group, prior to discharge from the clinic, vital signs should be recorded, and a review of AE(s) and concomitant medications should be conducted. Upon determination by the Investigator (or qualified designee) that the subject is stable, the participant will be discharged. If a participant experiences an unstable AE, the PI shall manage the event without prior consulting with the Medical Monitor. The MM shall be informed as soon as possible, and the management of the AE shall be reported in the Study documents.

For intense PK group, if no medical or compliance concerns are identified, the subject will be scheduled for the next day PK sampling unless patients prefer to complete end-of-trial visit in one day.

Day 2 (Intense PK only)

Patient should arrive in clinic fasted in the morning after an overnight fast but do not need to be in OFF state. The subject will start PK sampling phase, which entails the following procedures.

5. Place an intravenous line for blood sampling for the subgroup that will collect 10-hour blood samples.
6. Collect initial samples of blood (hour 0).
7. Administer last dose of assigned study drug after the hour 0 sampling.
 - a. For 16 subjects per group, their blood samples (10mL) will be collected at 1hr, 1.5hr, 2hr, 3hr, 4hr, 5hr, 6hr, 7hr, 8hr, 9hr, and 10hr. Blood should be taken within ± 10 mins of times.
 - b. Perform periodic safety monitoring during the collection period. Participants should be asked about pain, redness or swelling at the blood collection site in the arm.
 - c. Patients will be provided low-fat light meal after 2hr, 6hr and 10hr PK sampling. Sites should take detailed notes of contents of all meals provided to the patients.
8. Perform the final safety monitoring.

Prior to discharge from the clinic, vital signs should be recorded, and a review of AE(s) and concomitant medications should be conducted as the final safety monitoring. Upon determination by the Investigator (or qualified designee) that the subject is stable, the participant will be discharged. If a participant experiences an unstable AE, the PI shall manage the event without prior consulting with the Medical Monitor. The MM shall be informed as soon as possible, and the management of the AE shall be reported in the Study documents.

9.5.3. Post End of Trial Visit 24-Hour Phone Follow-up

Approximately 24 hours following the end of trial visit the subject will be contacted by phone to confirm the subject's well-being and to query about any new AEs.

9.5.4. After The Trial

The subject will continue the standard of care of Parkinson's disease under the supervision of the treating physician.

10.0 EARLY TREATMENT/STUDY DISCONTINUATION

The investigators at each site will make every reasonable effort to maximize subject retention. However, if an investigator removes a subject from treatment or study, or if a subject declines further treatment or study participation, an early discontinuation visit will be completed as soon as possible following discontinuation.

10.1. Reasons for Early Discontinuation

Participants may withdraw from the study at any time as stated in the informed consent document given to the participant at the time of enrollment. Participants must also be discontinued from treatment/study for reasons such as the following:

- Adverse experience: The participant has experienced an adverse event that, in the opinion of the investigator, requires early discontinuation. This may include abnormal laboratory values.
- Death.
- Safety risk: Any participant who becomes a safety risk to themselves or others during the trial will be withdrawn.
- Protocol violation: The participant fails to meet protocol entry criteria during the study after being randomized or does not adhere to protocol requirements.
- Development of suicidal or homicidal ideation requiring hospitalization or confinement.
- Consent is withdrawn. The participant wishes to withdraw from the study.
- The study is terminated by the Sponsor/Coordinating Center, alone or at the recommendation of the Data Safety Monitoring Board.
- Lost to follow up. Participant could not be recalled back to conduct follow up visits.

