7.8. Concomitant Medications

7.8.1. Prohibited Concomitant Medications

Investigational agents are prohibited 4 weeks or five half-lives, whichever is greater, prior to entry and for the duration of the trial.

Initiation of prohibited medications during the course of the study is discouraged, however, if an excluded medication is initiated after screening, the site should consult with the Project Directors and Medical Monitor for further guidance.

Buntnetap is mainly metabolized by CYP3A4 in vitro. Therefore, we recommend avoiding concomitant use of strong or moderate CYP3A4 inhibitor/inducers, examples see below according to FDA guidance on drug development and drug interactions.

CYP3A4 inhibitors	Itraconazole, Ketoconazole, Azamulin, Troleandomycin, Verapamil
CYP3A4 inducers	Rifampicin

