8.1. Inclusion Criteria

Subjects must meet the following criteria:

1. Diagnosis of idiopathic PD according to MDS Clinical Diagnostic Criteria for Parkinson's Disease ([Postuma 2015](#)).
2. H&Y score =1, 2 or 3 during ON-state & OFF-state <2hrs per day.
3. Male or female aged 40 – 85 years.
4. MMSE score between the range of 22-30 during screening visit (ON-state) and subjects can live independently without a caregiver.
5. Female subjects of childbearing potential* must have a negative urine pregnancy test at Screening, must be non-lactating and must agree to use a highly effective method of contraception (i.e., a method resulting in a failure rate of less than 1% per year when used consistently and correctly) during the trial and for 4 weeks after the last dose of trial treatment, such as:
 - Oral, intravaginal, or transdermal combined (estrogen plus progestogen) hormonal contraception associated with inhibition of ovulation
 - Oral, injectable, or implantable progestogen-only hormonal contraception associated with inhibition of ovulation
 - Intrauterine device (IUD)
 - Intrauterine hormone-releasing system (IUS)
 - Bilateral tubal occlusion
 - Vasectomized partner (a vasectomized partner is a highly effective contraception method provided that the partner is the sole male sexual partner of the participant, and the absence of sperm has been confirmed. If not, an additional highly effective method of contraception should be used)
 - Sexual abstinence (sexual abstinence is considered a highly effective method only if defined as refraining from heterosexual intercourse during the entire period of risk associated with the study treatment. The reliability of sexual abstinence needs to be evaluated in relation to the duration of the study and the preferred and usual lifestyle of the participant)

*Non-childbearing potential includes surgically sterilized or postmenopausal with no menstrual bleeding for at least one year prior to study start.

6. Male subjects must be sterile or sexually inactive or agree not to father a child during the study and one month after the last dose of study medication and must agree to use a barrier method for contraception. Female partners of male subject must adopt a highly effective method of contraception with a failure rate of less than 1% per year when used consistently and correctly such as:

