12.1.2. Electrocardiogram (ECG)

An appropriately qualified individual will conduct a standard 12-lead supine resting ECG. The ECG report must be reviewed, signed, and dated by the site PI (or a medically qualified individual delegated by the site PI). Those with clinically significant ECG findings will be referred for follow-up as deemed appropriate by the investigator and may be excluded from the study.

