12.1.3. Clinical Laboratory Evaluations

Blood and urine samples will be obtained for clinical safety lab assessments as described in the Schedule of Events ([Appendix 1](#)). The following table lists the clinical safety lab tests that will be assessed by the central lab at these time points: the screening visit, each clinical visit (1 month, 2 months and 3 months), and the end of trial visit. Refer to the Laboratory Manual for additional details.

CLINICAL SAFETY LAB TESTS		
METABOLIC PANEL	COMPLETE BLOOD COUNT	URINALYSIS
Sodium (Na)	White Blood Cell Count (absolute and percentage): basophils, eosinophils, lymphocytes, monocytes, neutrophils	Color
Potassium (K)		Appearance
Chloride (Cl)		Specific Gravity
Carbon Dioxide (CO2)	Red Blood Cell Count (RBC)	pH
Blood Urea Nitrogen (BUN)	Hemoglobin (Hb)	Blood
Glucose	Hematocrit (HCT)	Glucose
Calcium (Ca)	Mean Corpuscular Volume (MCV)	Protein
Creatinine (Crn)	Mean Corpuscular Hemoglobin (MCH)	Ketones
Bilirubin (direct and Total)	Mean Corpuscular Hemoglobin Concentration (MCHC)	Leukocyte Esterase
Albumin	Red Blood Cell Distribution Width (RDW)	Nitrite
Protein - Total	Mean Platelet Volume (MPV)	Urobilinogen
Glutamic-Oxaloacetic Transferase (AST, SGOT)	Platelet Count (PLT)	Bilirubin (total)
Glutamic-Pyruvate Transferase (ALT, SGPT)		
Alkaline Phosphatase (ALP)		
eGFR (estimated Glomerular Filtration Rate)	Screening Only Hemoglobin A1C (HbA1c)	

Lab reports will be reviewed, signed, and dated by the site PI (or a medically qualified individual delegated by the PI). If a value is outside of the laboratory's normal range, the clinician will indicate if the value has clinical significance. Those results that are deemed clinically significant may need to be repeated and may require follow up with the subject's primary care physician for further evaluation.

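### Protocol 10.1 mandates removal from treatment/study for events that 7.8.1, 7.6 and its own adverse-experience bullet leave to judgement, and removal before month 5 costs the Month 6 primary score

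*Protocol*

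**What the plan says.** The list in Protocol 10.1 opens: "Participants must also be discontinued from treatment/study for reasons such as the following". Its protocol-violation bullet begins: "The participant fails to meet protocol entry criteria during the study after being randomized". The second half of the bullet adds failure to follow the protocol. That bullet has no judgement qualifier. The adverse-experience bullet in the same list does: it applies to an event that, "in the opinion of the investigator, requires early discontinuation. This may include abnormal laboratory values".

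Elsewhere the protocol handles overlapping events differently:

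- 7.8.1, on excluded drugs: "if an excluded medication is initiated after screening, the site should consult with the Project Directors and Medical Monitor for further guidance".
- 7.6 treats removal for insufficient compliance as something that may happen, not as a requirement.
- 12.1.2, on subjects with clinically significant ECG findings: they "will be referred for follow-up as deemed appropriate by the investigator and may be excluded from the study".
- 12.1.3, on laboratory values: "Those results that are deemed clinically significant may need to be repeated".

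Protocol 10.0 sends a subject removed from either treatment or study to an Early Discontinuation visit. Note e to the Schedule of Events limits this to those leaving before 5 months; later leavers have the full End of Trial visit. In both the protocol and SAP schedules, MDS-UPDRS is marked at baseline and Months 1, 2, 3 and 6, and not at the Early Discontinuation visit.

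**The concern.** Two sites facing the same event could act differently and each cite the protocol. One would remove the subject under 10.1. The other would consult under 7.8.1, or use its own judgement under the adverse-experience bullet.

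The statistical cost comes from the term treatment/study, which treats stopping drug and leaving follow-up as one act. A subject taken out before month 5 for an entry-criterion departure provides no further MDS-UPDRS assessments. The Month 6 Part II score is then missing because of a procedural rule, even if the subject would have been willing to attend. The primary MMRM assumes data are missing at random (SAP 8.9). If the reason for removal is related to the outcome or to treatment, that assumption is strained by losses that could have been avoided.

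**Working it through.** **1. The passages side by side.**

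| Event after randomisation | Entry criterion or requirement | Protocol-violation bullet, 10.1 | Other text | Relation |
|---|---|---|---|---|
| Strong or moderate CYP3A4 drug started | Exclusion 16 | must be discontinued | 7.8.1: consult | Direct conflict |
| Poor compliance with study drug | Second half of the 10.1 bullet | must be discontinued | 7.6: possible | Direct conflict |
| Clinically significant laboratory value | Exclusion 7 | must be discontinued | 10.1 adverse-experience bullet: investigator's opinion | Conflict within 10.1 |
| Same | Exclusion 7 | must be discontinued | 12.1.3: repeat, follow up | Tension only; 12.1.3 is silent on discontinuation |
| QTcF at or above the limit | Exclusion 3, not tied to screening | must be discontinued | 12.1.2: may be excluded | Tension only; 12.1.2 names no visit and could refer to entry |

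Exclusion 4 (heart rate) is expressly tied to the screening ECG, so it cannot newly fail later. The ECG overlap is therefore mainly with exclusion 3.

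**2. From removal to missing score.** The 10.1 bullet removes the subject from treatment/study. Under 10.0 and note e, a subject leaving before month 5 has the Early Discontinuation visit. That visit has no MDS-UPDRS, so no Month 6 Part II score exists. Scores already taken at Months 1 to 3 stay in the MMRM, and the Month 6 mean rests on missing at random.

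**3. Could disease worsening trigger the bullet?** Inclusion 2 requires "H&Y score =1, 2 or 3 during ON-state & OFF-state <2hrs per day" and is not tied to screening. Read literally, worsening past it means entry criteria are no longer met. However, the Hoehn & Yahr stage is scheduled only at screening, eligibility is reviewed only at screening and baseline, and the MMSE range in inclusion 4 is tied to the screening visit. No scheduled step re-applies the criteria after baseline.

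**4. Scale.** This point disputes no figure in the plan. For background, the stated 90% power (SAP 8.10.2: 174 per arm, difference 3, SD 8, two-sided alpha 0.025) reproduces:

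- Power = Φ(3 / (8 × √(2/174)) − 2.241) = Φ(3.498 − 2.241) = 0.8955.

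SAP 8.10.2 reports blinded dropout of about 6% from all causes. Suppose, as an extreme, that all of it came from this bullet and that each lost subject contributed nothing:

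- n = 174 × 0.94 = 163.6 per arm; power = Φ(3 / (8 × √(2/163.6)) − 2.241) = 0.875.

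Loss of numbers is therefore a small matter. Any real harm would come from which scores are missing, and the documents give no count of removals under this bullet.

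**The case against.** The strongest reply has four parts.

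**The list is illustrative and headed as a protocol violation.** The words *such as* leave the list open to additions, but they do not make a listed reason optional. The heading does help: natural worsening of disease is not obviously a violation. That weakens the progression reading, but not the conflict over excluded drugs or compliance.

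**The SAP already covers such subjects.** SAP 8.3.5 provides for discontinuation reasons by treatment group. SAP 8.9 applies control-based multiple imputation under missing not at random to subjects who do not complete, whatever the reason. This stands, and no new sensitivity analysis is needed. It limits the damage from missing scores but does not recover them.

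**The missing score comes from the Early Discontinuation visit, whatever the reason for leaving.** That is correct. This bullet matters because it can send to that visit subjects who need not have left follow-up.

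**The change comes late.** Enrolment was complete on 9 June 2023 and the SAP is dated 11 January 2024. This also stands.

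A reader might go further and infer that 10.1 systematically removes subjects whose Parkinson's disease progressed, and so biases the result appreciably. The documents do not support that. Take bias ≈ (placebo share removed − active share removed) × unobserved shift in Part II, with every input assumed:

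- Shares 5% and 2%, shift 4 points: 0.03 × 4 = 0.12 points; pooled removal (5 + 2 + 2)/3 = 3.0%.
- Shares 10% and 4%, shift 6 points: 0.06 × 6 = 0.36 points; pooled removal (10 + 4 + 4)/3 = 6.0%.
- Shares 10% and 5%, shift 4 points: 0.05 × 4 = 0.20 points; pooled removal (10 + 5 + 5)/3 = 6.7%.

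The second case needs every reported dropout to be a progression removal, and the third exceeds the reported total. The first needs half of it. Nothing in the documents indicates that any dropout arose this way.

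**Conclusion.** The inconsistency is real. It is direct for 7.8.1 against exclusion 16, for 7.6 against the second half of the bullet, and within 10.1 for laboratory values. Sections 12.1.2 and 12.1.3 are in tension with the bullet but not directly contrary to it.

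The consequence for the primary endpoint follows from the text: a subject removed under this bullet before month 5 has no Month 6 Part II score. Removal for disease worsening is possible on a literal reading of inclusion 2, but the plan does not put it into operation.

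Neither the number affected nor the bias can be estimated from the documents. The only anchor is the all-cause blinded dropout of about 6%, which was seen at a blinded data review and may differ from the final figure. That low rate gives no sign that the mandatory reading was widely applied; it does not show that sites applied one rule consistently.

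**What to change.** 1. Reconcile the protocol-violation bullet in 10.1 with 7.8.1, 7.6 and the adverse-experience bullet, and align 12.1.2 and 12.1.3, so that one rule applies to each event. Which treatment-stopping rule is right is a clinical decision on which this review takes no view.
2. In that bullet, separate *treatment* from *study*, and align 10.0 with it. State that a post-randomisation departure from an entry criterion does not by itself end the scheduled efficacy assessments to Month 6 for participants who still consent.
3. Optionally, within the disposition output already planned in SAP 8.3.5, list discontinuations under this bullet by arm and by the criterion concerned.

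The cost is a wording amendment, a few subjects followed at visits already scheduled and, if item 3 is adopted, extra rows in an existing table. With enrolment closed by June 2023, items 1 and 2 may help few current subjects. Item 3 would still show how often the bullet was used, and in which arms.
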